Overview of methods: Work package 1 will use a combination of quantitative analysis of existing data sources, and qualitative research. The first research question will use data from the NHS DPP and existing administrative data sources to explore access. Research question 4 will explore if access is influenced by the understandings and experiences of participants.

When the initial research proposal was written, the National Diabetes Audit data was not considered useful, as at that point in time it did not contain data on non-diabetic hyperglycaemia. This information has since been added to the National Diabetes Audit. The National Diabetes Audit offers a more complete coverage of general practice than CPRD data, and so will now replace the CPRD analysis which was originally planned (conditional on checks of completeness and quality of the NDA).

Research question WP 1.1: Are there inequalities in the identification of patients eligible for the NHS DPP? Is there an under-representation of participants with protected characteristics in general practice compared to the general population of adults at risk of diabetes?

Methods: We will compare the characteristics of patients identified with non-diabetic hyperglycaemia in GP patient records (using the National Diabetes Audit dataset, NDA) to the characteristics of patients identified with non-diabetic hyperglycaemia in representative survey data for England.

The English Longitudinal Study of Ageing (ELSA); Understanding Society and the Health Survey for England (HSE) surveys record HbA1c test results (enabling an assessment of non-diabetic hyperglycaemia) and contain comparative measures of social class (sourced via Lower Super Output Area (LSOA) IMD score with LSOA and/or IMD score obtained via special access license), ethnicity, sex, and disability status. Multivariable probability analysis will be used to test if the probability of having non- diabetic hyperglycaemia differs across surveys for particular patient characteristics. ^{66 67} This analysis will identify whether patients identified as non-diabetic hyperglycemic in primary care records differ from those in nationally representative surveys. We will use:

- a) Understanding Society waves 2 and 3 (2010-2012). All adult respondents are surveyed but blood samples were taken of 13,107/35,937 eligible (12,162 instances of HbA1c (mmol/mol) being recorded), all ages 16 and over, 964 participants with HbA1c between 42-47 mmol/mol

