Research question WP 5.1 – What is the current epidemiology of non-diabetic hyperglycaemia and diabetes?

This work package will investigate rates and patterns of non-diabetic hyperglycaemia and its conversion into a diabetes diagnosis, to provide critical background information for the interpretation of findings related to the effects of the NHS DPP.

Methods: We will investigate the prevalence and incidence of non-diabetic hyperglycaemia using a specific list of Read codes which are routinely used in UK primary care. ⁹⁷ A preliminary analysis using CPRD shows that the use of the codes has increased considerably over time. For the latest period (April 2015 to March 2016), at least one relevant code was found in the records of 71,521 patients (1.57%), implying around 900,000 people nationally with non-diabetic hyperglycaemia.

We will also estimate the association between diabetes and non-diabetic hyperglycaemia prevalence at the practice level. We expect a strong correlation which would indicate that diabetes data can be used as a reasonable proxy in the absence of data on non-diabetic hyperglycaemia data.

From 2016-17 onwards, we will use these historical codes and the new codes that will be introduced with the NHS DPP programme to calculate and report detailed information on non-diabetic hyperglycaemia. Excluding cases with an existing diabetes diagnoses, we will calculate both the prevalence and incidence of non-diabetic hyperglycaemia over time, nationally and regionally (such as CCGs or NHS England Local Area Teams). To better understand regional variation, we will calculate age-sex standardised prevalence and incidence rates. We will use longitudinal multivariable mixed-effects regression models to identify predictors of non-diabetic hyperglycaemia from a list of relevant covariates: age, sex, deprivation and QOF comorbidities (excluding diabetes mellitus). 98 99 We will investigate changes in the characteristics of the non-diabetic hyperglycaemia populations over time, by including time interaction terms in the regression models.

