We will use an interrupted time-series design² to quantify the overall effect of the introduction of the NHS DPP on the prevalence and incidence recording of non-diabetic hyperglycaemia (overall and regionally). This is a quasi-experimental design which we have applied in a number of previous studies, most notably to evaluate the impact of the QOF. ^{93 100 101} Using a mixed-effects regression model we will control for any changes in the population demographics over time, to obtain a more reliable effect estimate. ¹⁰² This design assumes a linear pre-intervention trend, which seems plausible according to our initial modelling. Nevertheless, we will statistically assess linearity and if rejected we will use alternative models with non-linear terms for prevalence of non-diabetic hyperglycaemia.

More inclusive criteria in the Health Survey for England have returned much higher prevalence estimates for non-diabetic hyperglycaemia, and we will explore implementing them to obtain more speculative estimates through which to conduct sensitivity analyses (i.e. based on HbA1c values and relevant Read codes). However, for the purposes of all planned analyses in this and other work-packages, this is a relatively minor issue (except regarding the true non-diabetic hyperglycaemia prevalence rate). For example, the predictors of non-diabetic hyperglycaemia should be consistent across the two analyses (of conservative or more speculative cases) since we would not expect systematic bias in relation to the research questions (i.e. the predictors of non-diabetic hyperglycaemia should be the same whether a large percentage of patients is missed, or not). Even in there is some form of systematic bias (for example if Read code cases are more 'severe'), the findings from the conservative analysis would still be relevant and important. Finally, it might be the case that a conservative approach where we focus on definite non-diabetic hyperglycaemia cases which have been coded as such may be more desirable.

Research question WP 5.2 - What is the effectiveness of the NHS DPP at reducing the conversion of non-diabetic hyperglycaemia to diabetes?

The primary objective of the NHS DPP is to reduce, or at least slow, the rate at which patients with non-diabetic hyperglycaemia go on to develop a full diabetes diagnosis. In line with this, the main outcome in these analyses will be the conversion of non-diabetic hyperglycaemia to diabetes.

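### WP 5.1 assumes that predictors of GP-coded non-diabetic hyperglycaemia are unaffected by missed cases; that needs coding to be unrelated to the modelled covariates, which the protocol itself gives reason to doubt

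*Protocol*

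**What the plan says.** Under Research question WP 5.1, Methods, the case definition is a code list: "We will investigate the prevalence and incidence of non-diabetic hyperglycaemia using a specific list of Read codes which are routinely used in UK primary care". For 2015-16, "at least one relevant code was found in the records of 71,521 patients (1.57%), implying around 900,000 people nationally with non-diabetic hyperglycaemia". The protocol adds: "A preliminary analysis using CPRD shows that the use of the codes has increased considerably over time". Longitudinal mixed-effects models will then identify predictors of NDH among age, sex, deprivation and QOF comorbidities other than diabetes. Time interactions will show how the NDH population changes.

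Later in WP 5.1 the protocol concedes that Health Survey for England criteria give much higher prevalence. It treats this as minor for every planned analysis except the true prevalence rate, on the ground that "the predictors of non-diabetic hyperglycaemia should be the same whether a large percentage of patients is missed, or not". It intends to explore a definition using HbA1c values together with codes for sensitivity analyses. It also says that code-based findings would keep their value if some systematic bias existed.

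WP 1.1 asks whether identification of eligible patients is unequal across groups. It compares GP-recorded NDH with NDH measured in surveys: "This analysis will identify whether patients identified as non-diabetic hyperglycemic in primary care records differ from those in nationally representative surveys". One survey, Understanding Society, contributes "964 participants with HbA1c between 42-47 mmol/mol" out of 12,162 recorded HbA1c results.

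**The concern.** A patient enters the WP 5.1 outcome only after three things have happened: they have NDH, they were tested, and the result was coded. A regression on that outcome estimates how covariates relate to all three together. Missing many cases is harmless to the associations only if testing and coding are equally likely at every level of the covariates.

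If they are not, a group that is under-identified looks like a group at lower risk. Because code use has been rising, the time interactions may likewise pick up changes in recording rather than in who has the condition. The results would be presented as predictors of NDH. They are meant as background for interpreting the programme's effects, and WP 5.3 plans forward projections that draw on the team's NDH incidence estimates, so the label matters to later readers.

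**Working it through.** **1. What the assumption requires.** Let p be true prevalence in a group and s the probability that a true case is coded. Recorded prevalence is p × s. For an uncommon outcome, the recorded odds ratio is therefore about (s₁/s₀) × the true odds ratio. It equals the true value only if s₁ = s₀ across levels of the covariate.

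**2. What the protocol says about s.**
- Background and Rationale: people with NDH are found through NHS Health Checks and primary care registers.
- Work package 1, Rationale: previous research shows that age, gender and socio-economic status, among other factors, affect attendance at NHS Health Checks.
- WP 5.1, Methods: age, sex and deprivation are modelled as predictors.
- WP 1.1: whether identification is unequal is an open research question.

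So the protocol itself links one named route to identification with factors that match, or closely parallel, three of the modelled predictors. It offers no evidence that s is constant.

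**3. The plan's own prevalence figure.** 71,521 / 0.0157 = 4.56 million patients in the base. The national figure of 900,000 implies 900,000 / 0.0157 = 57.3 million people. The protocol does not state that population, so the extrapolation cannot be strictly reproduced. Nothing below depends on it.

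**4. Share of cases coded.** Measured prevalence (Understanding Society, 2010-12, age 16 and over, unweighted) is 964 / 12,162 = 7.93%.

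| Comparison | Calculation | Coded | Uncoded |
|---|---|---|---|
| Figures as stated | 1.57 / 7.93 | 19.8% | 80% |
| Coded rate put on an adult base (assume 81% of patients are 16+) | (1.57 / 0.81) / 7.93 | 24.5% | 76% |
| As above, and assume a quarter of survey cases have known diabetes | (1.57 / 0.81) / (7.93 × 0.75) | 32.6% | 67% |

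The 81% and the one-quarter are assumptions, not protocol figures.

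**5. What differential coding could do.** The coding rates below are assumed. The first three rows use p = 7.93% in both groups. The last three use p₀ = 7% and a true odds ratio of 1.50, so the odds are 1.5 × 0.07/0.93 = 0.1129 and p₁ = 10.14%.

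| True OR | s₁ vs s₀ | Recorded OR |
|---|---|---|
| 1.00 | 24% vs 20% | 1.20 |
| 1.00 | 30% vs 20% | 1.51 |
| 1.00 | 30% vs 15% | 2.02 |
| 1.50 | 22% vs 22% | 1.46 |
| 1.50 | 18% vs 26% | 1.00 |
| 1.50 | 15% vs 30% | 0.72 |

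For the second row, recorded prevalences are 7.93 × 0.30 = 2.38% and 7.93 × 0.20 = 1.59%, and the ratio of their odds is 1.51. Equal coding roughly preserves the association; unequal coding creates, hides or reverses it. The low overall coding rate does not itself cause the bias, but it leaves ample room for groups to differ.

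**The case against.** The wording in WP 5.1 is an expectation, not a guarantee. The same paragraph allows for systematic bias and mentions an HbA1c-based analysis. One work package expecting what another tests is not in itself a contradiction. WP 5.1 is background work, and the main outcome of WP 5.2 is conversion to diabetes among identified cases. The comparison of 1.57% with 7.9% crosses years and age bases. The survey took blood from 13,107 of 35,937 eligible people. It is also unclear whether the 71,521 are patients with a code entered in that year or with any code on record; if the former, cumulative coding is higher.

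Much of this stands, and it rules out several stronger readings that a reader might infer:
- *That bias of a known size will occur.* The protocol gives no coding rates by group, so 1.51 is an illustration.
- *That the equity results are compromised.* WP 1 compares audit records with surveys directly and does not use WP 5.1 estimates.
- *That the interrupted time series is mislabelled.* It already names recording of prevalence and incidence as its outcome. The predictor models and their time interactions do not.
- *That a value-based definition must replace the codes.* HbA1c values exist only for people who were tested, so part of the same selection remains, and the protocol gives a reason to prefer definite, coded cases.

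The caveats do not rescue the statement itself. The only example of bias offered is severity, not coding that depends on the covariates. The sensitivity analysis is something to explore rather than a commitment. Saying that the findings remain useful does not settle what they measure.

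**Conclusion.** The statement that predictors are unaffected by missed cases is unsupported and should not stand. It rests on coding being independent of age, sex, deprivation and comorbidity. The protocol gives reason to doubt this for the first two, and for socio-economic status as the counterpart of deprivation; WP 1.1 leaves unequal identification open. For comorbidity the documents are silent either way. On the protocol's counts, about 67% to 80% of cases are uncoded, subject to the differences in year, age base and known diabetes set out above. Followed as written, WP 5.1 would present associations with recorded NDH as predictors of NDH. The direction and size of any distortion cannot be derived from the protocol. The point affects the interpretation of the predictor and time-interaction models; it does not show that the WP 1 or WP 5.2 results are wrong.

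**What to change.** - Delete the invariance statement in WP 5.1, or make it conditional on the WP 1.1 result.
- Label the code-based predictor and time-interaction results *predictors of recorded NDH*.
- Commit to the HbA1c-value-plus-code analysis as a side-by-side sensitivity analysis, noting that it still depends on who is tested.
- For the covariates shared with the surveys (age, sex, deprivation), report the WP 5.1 associations beside the survey-measured associations from WP 1.1, and limit claims about NDH risk where they disagree.

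The code-based definition may remain the main one. The cost is a wording change, a modest amount of extra analysis and a narrower conclusion. The survey comparison draws on data that WP 1.1 already plans to use, including deprivation scores under special licence. Strict agreement with the surveys should not be required: the numbers with measured NDH are limited (964 in Understanding Society), and ELSA covers only people aged 50 and over.

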- b) ELSA adults aged 50+ with 457 wave 2 participants, 1,297 wave 4 participants, 1,315 wave 6 and 806 wave 8 participants with HbA1c between 42-47 mmol/mol
- c) NDA (comparative observable factors e.g. age, gender, IMD, comorbidity; flags for non-diabetic hyperglycaemia)

Research question WP 1.2: Are there inequalities in the referral of patients to the NHS DPP?

Once a diagnosis of non-diabetic hyperglycaemia has been made, the GP may or may not refer the patient to NHS DPP. This decision to refer may be influenced by both the GP and patient, and may be related to patient or professional perceptions of the value of the service.

Method: We will compare the observable characteristics of patients referred to the NHS DPP in the Minimum DataSet (MDS) to patients identified with non-diabetic hyperglycaemia in the NDA dataset and those in surveys using analogous methods as those described in WP 1.1. The MDS contains information that providers of the DPP are contractually obliged to collect in order to receive financial reimbursement. It contains dates and sources of referrals and information about subsequent programme attendances, as well as participant outcome measures, as recorded by the providers of the programme.

Research question WP 1.3: Are there inequalities in attendance and completion of the NHS DPP?

Following a positive identification of non-diabetic hyperglycaemia, patient uptake and adherence to the NHS DPP intervention may vary. We can examine this in the MDS, using relevant codes for 'referral to the NHS DPP intervention', 'intervention started', 'declined' and 'completed'.

Method: Using MDS data (observable patient characteristics e.g. age, gender, IMD, co-morbidities). for those referred and on the programme we will compare the characteristics of patients and how this varies with course uptake and completion, the characteristics will be compared to patient characteristics in the NDA and survey datasets to understand at what point the characteristics of patients begins to change.

Research question WP1.4 What is the experience of patients and professionals in accessing the NHS DPP?

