To recruit patients, we will use two methods: (a) Researchers will attend the practices on agreed days for study recruitment (b) Practice staff recruit and consent patients.

We know that some practices may want to recruit and consent patients into the study without the presence of a researcher. This method of recruitment was suggested by GPs involved in another diabetes prevention study (14/SC/0097), as diabetes prevention advice is sometimes provided ad hoc.

In this method, primary care staff will answer any questions about the study, go through the Patient Information Sheet, and consent patients once they have understood the study.

Using the above strategies, patients will be provided with all necessary information about the study so they can make sure participation is right for them. Also, patients will be made aware of their right to withdraw their data and participation from the study at any time.

We are aware that some patients may enter the NHS DPP through routes other than primary care, such as response to adverts. If many sites are using referral options other than primary care, we will work with NHS DPP providers to recruit these patients to understand their experience of accessing the course. In these cases, we would ask the NHS DPP providers to send patients an invitation letter and a Patient Information Sheet, and ask those patients to return a 'consent to contact' form if they are willing to be interviewed

We will interview all professionals (n=10) after consultations and a proportion of patients (approximately 20) to gauge understanding of levels of risk and the meaning of relevant diagnostic information, as well as both perspectives on any decisions about referral and need for the NHS DPP intervention. We will follow the approach of our previous research^{72 73} to analyse observations alongside interviews to explore influences associated with access and use of the NHS DPP.

Additionally, we will interview people with a Read code for non-diabetic hyperglycaemia ('NHS DPP eligible' patients), but who have not been referred to the DPP. We will also include people for whom referral has been offered but declined ('NHS DPP attenders'). We will work with practices to identify such patients from their primary care records. Practices will send patients an invitation letter and patients who agree to participate will complete and return 'consent to contact form'.

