Methods: The primary analysis for assessing the effectiveness of the NHS DPP will use the NDA+MDS if assessed as fit for that purpose, otherwise the work will be done in the CPRD. For robustness, we will address the question using two different research designs.

WP 5.2 design 1: We will use all practices participating in the NHS DPP, and compare the conversion rate from non-diabetic hyperglycaemia to diabetes in patients prior to the start of the NHS DPP to the rate afterwards in equivalent patients. To accomplish this, we will match pre-intervention cases of non-diabetic hyperglycaemia ⁹⁷ to post-intervention cases at the same practice and with the same practitioner if possible (excluding cases with a previous diabetes diagnoses). We will then compare the rates of conversion to diabetes within 2 years between these groups.

Earlier, we confirmed that risk-of-diabetes Read codes are already routinely being used. As the NHS DPP-specific Read codes are not available for patients prior to the scheme, we will conduct an initial exercise to identify the group of pre-existing codes that best identify patients classed as eligible using the NHS DPP-specific codes. We will then use the identified codes to classify patients as scheme-eligible both pre- and post-NHS DPP, to ensure comparability. We will use propensity score methods for the matching. In the logistic regression model to calculate the score we will include: age, sex, region, deprivation, QOF comorbidities and all available biological parameters (e.g. body mass index and HbA1c levels at baseline). Data will be complete for all covariates except the biological parameters, for which we expect a very high level of completeness for this group of patients.

Nevertheless, we will use appropriate multiple imputation methods for longitudinal data if needed. 103

We will compare the conversion rates to diabetes between the two matched groups. Since practices are unlikely to refer all their cases of non-diabetic hyperglycaemia to the scheme (because of capacity limits), we will also compare those patients who were referred to their matched pre-intervention controls, while recognising that this comparison will be subject to confounding with any selection bias.

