We will explore a number of secondary outcomes. For hospitalisation, we will use all cases of hospitalisation and cases where the main reason for hospitalisation was diabetes, within 2 years of the index date (referral to the scheme). For primary care visits, we will use all visits to primary care within 2 years of the index date. For biological parameters (HbA1c and BMI) we will use the last available measurement within 1 year and 2 years of the index date (since HbA1c and BMI are expected to respond within a shorter period). We have developed relevant methodologies for BMI prediction and have used other methodological tools for multiple imputation of missing data, which we will consider using in this context.

All analyses will be repeated for the secondary outcomes with small changes in the analytic models: Poisson regressions for hospitalisations and primary care visits; linear regressions for HbA1c levels and weight/BMI; Cox proportional hazards regression for deaths. Sensitivity analyses will be used to assess the robustness of the results to different assumptions about patient eligibility, choice of covariates, and modelling options (e.g. multivariable regression instead of matching).

WP 5.2 design 2: For this analysis, we will only use data from the post-intervention period and compare non-diabetic hyperglycaemia-to-diabetes conversion rates. Our main analyses will involve within practice matching, of patients referred to the scheme versus matched patients not referred. However, we will also use across practice matching to control for potential unmeasured confounding in referrals, by matching referring practices to non-referring practices over a set time period, before matching referred patients (from the referring practice) to non-referred patients (from the matched non-referring practice). In the within practice matching we will match patients on age, sex, time of NDH diagnosis and practice. We will attempt to include more controls to increase power (5 to 1, if

possible). In the across practice matching we will match referring to non-referring practices within each English region, and patients will be matched on age, sex and time of NDH diagnosis.

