- 1. Patient experiences of the process prior to referral to the DDPP including discussions in primary care about the DDPP, any alternative programmes discussed or offered, reasons for refusing face-to-face DPP (if applicable).
- 2. How and why patients choose to accept or decline referral to a digital programme, and how this differs from decision-making around the face-to-face programme;
- 3. How and why patients initially engage with the DDPP, including their experience of the referral and on-boarding process:
- 4. Patient perceptions of the advantages and disadvantages of embarking on the DDPP, perceptions of the advantages and disadvantages of embarking on the face-to-face programme, perceptions of the aim and scope of the DDPP, and expectations about potential impact of the DDPP on their personal health behaviours.

METHODS

Design: Qualitative study using semi-structured interviews with patients/service users.

Setting: The re-procured DPP is intended to cover the whole of England from August 2020. Five providers have been selected to deliver the DDPP and each local health service has chosen one or other of these providers. There are several pathways of referral into the DDPP:

Primary care referrals:

The original pathway for DDPP delivery was through primary care. Patients identified with pre-diabetes (determined by an eligible HbA1c reading in the last 12 months) by their general practice would be offered the face-to-face version of the DPP, either by letter or during consultations with health professionals. If a patient declined this offer of face-to-face DPP they would be offered it again on a further two occasions. If the patient declined face-to-face three times, then they were eligible to be offered DDPP by their health professional. There was also a cap of 20% of patients who could be referred to DDPP. Following the closure of many GP practices due to Covid-19 and subsequent pausing of the face-to-face version of the DPP, changes were made to the way that the DPP was offered to patients.

i. A 'remote group' service has been developed, with group sessions delivered via online platform or via telephone for patients without access to a webcam.

- ii. In primary care patients are now offered a choice of 'remote group' or DDPP from the first offer (removing the need to have declined face-to-face before being offered DDPP).
- iii. The cap of 20% was removed so that all eligible patients could be offered the DDPP.

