- iv. Eligibility criteria has been changed to allow patients with an eligible HbA1c reading within the last 24 months (instead of 12 months) to be contacted through primary care and offered 'remote group' or DDPP.

Once patients have been identified in primary care there are two main ways of them accessing the DDPP: a) Practices identify eligible patients and send letters explaining their risk of diabetes and offering the DDPP. Patients are asked to call the service provider of the DDPP to register. b) The DDPP is offered opportunistically by practices to patients during appointments, and a letter is sent to the provider by the practice.

Service providers of DDPP:

The changes to the referral route due to Covid-19 now allow service providers of the DDPP to directly contact patients who have previously declined offers of face-to-face from their own lists and offer them access to the DDPP.

Self-referral:

In August 2020, in response to the COVID-19 pandemic, the DDPP expanded access by moving from a referral only route (from general practice) to add a self-referral route via an online risk tool. Eligibility to self-refer into the programme is based on the Diabetes UK risk tool (a validated Type 2 diabetes risk assessment tool) which can be completed on the Diabetes UK website or on DPP providers' websites. People scoring at or above a risk threshold are signposted to self-refer with their local DPP provider (identified by postcode). Anyone scoring at or above the risk threshold is eligible to join provided they are aged 18-79, not pregnant and that they do not have a current Type 2 diabetes diagnosis. Once people have registered with the providers, they will be contacted to complete their registration. The providers will offer a choice of 'remote group' or DDPP. National and local advertising campaigns are currently advertising the risk tool.

Population: The target population for this study will be:

- Adults, aged 18 or over;
- Identified as having -nondiabetic hyperglycaemia, in accordance with the specification from NHSE; or identified as being at risk of developing type 2 diabetes in accordance with the 'Know your risk score'
- Offered, referred or self-referred to the DDPP
- · Both those who accept and decline the DDPP

Recruitment: We will aim to recruit up to 30 patient/service user (terms used interchangeably) participants from across the five providers.

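### WP5.2 design 2 and WP1.2 set no test-recency condition on their comparators, so people who were not referable at the index date can enter them

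*Protocol*

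**What the plan says.** **Entry rule.** WP9.3 (Setting, primary care referrals) says practices offered the programme to people with pre-diabetes "determined by an eligible HbA1c reading in the last 12 months". Item iv of the Covid-19 changes altered the criteria to "allow patients with an eligible HbA1c reading within the last 24 months (instead of 12 months"). The same section adds self-referral on an online risk score from August 2020, which needs no reading.

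**WP5.2 design 2.** Referred patients are compared with non-referred ones: "In the within practice matching we will match patients on age, sex, time of NDH diagnosis and practice". The across-practice version first pairs referring with non-referring practices within region, then matches patients on age, sex and time of diagnosis. HbA1c is not among the matching variables.

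**WP1.2.** Patients referred to the programme are compared "to patients identified with non-diabetic hyperglycaemia in the NDA dataset" and with survey respondents. No date window is attached to the NDA group.

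**WP5.2 design 1.** The team will first "identify the group of pre-existing codes that best identify patients classed as eligible using the NHS DPP-specific codes". It continues: "We will then use the identified codes to classify patients as scheme-eligible both pre- and post-NHS DPP, to ensure comparability". The propensity score includes "all available biological parameters (e.g. body mass index and HbA1c levels at baseline"). A further comparison sets referred patients against their matched pre-intervention controls.

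**Index date.** The only one given in WP5.2 is in the secondary-outcomes paragraph, and it is referral to the scheme.

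**The concern.** Under the rule in WP9.3, a patient referred through primary care has a recent reading in the NDH range, so diabetes was recently ruled out. Nothing in the design 2 matching or the WP1.2 denominator asks the same of the comparator. Such a patient may have been coded some years ago and not retested. The latest reading may have returned to normal, or already lie in the diabetic range without a diabetes code.

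In design 2, matching on time of diagnosis does not close the gap. Take two patients coded three years ago in the same practice. The referred one has a recent in-range test, while the control may have had none since coding. They can differ in underlying risk and in the chance that a conversion is recorded, for reasons unrelated to the programme.

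In WP1.2, the work package separates identification (WP1.1) from referral (WP1.2). If one group is retested less often, fewer of its coded members are referable. A gap in testing is then reported as an inequality in referral.

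**Working it through.** **1. The planned contrast.** WP5.2 (Sample size) assumes 2-year conversion of 7.5% against 5.625%, a 25% relative reduction or 1.875 points, with 90% power, 5% alpha and 1:1 allocation. The two-proportion formula

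n = [z₀.₉₇₅·√(2p̄(1−p̄)) + z₀.₉₀·√(p₁(1−p₁) + p₂(1−p₂))]² / (p₁−p₂)²

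with p₁ = 0.075, p₂ = 0.05625 and p̄ = 0.065625 gives 3,664 per group, or 7,328 in total. The protocol states 7,331, so the figure reproduces. The point here is one of definition and not of arithmetic.

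**2. The rules side by side.**

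| Comparison | Reading required of referred patients (primary care route, per WP9.3) | Reading required of comparator |
|---|---|---|
| WP1.2, NDA group | In range, within 12 then 24 months | None beyond being identified with NDH |
| Design 2, both versions | In range, within 12 then 24 months | None beyond matched time of diagnosis |
| Design 1, main pre/post | Not applicable: all code-eligible patients | Same calibrated codes in both periods |
| Design 1, referred against pre-intervention | In range, within 12 then 24 months | Codes, with HbA1c as a score covariate |

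The first, second and fourth rows are asymmetric. In the third, old codes can sit on both sides. They may dilute the contrast, but they do not by themselves create a difference between periods.

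**3. What this could do to design 2.** Let r be the share of controls who were not referable and k their conversion risk relative to referable controls. Both are assumptions, because the protocol gives neither. Control risk is 7.5% × [(1−r) + rk]. If the programme truly takes 7.5% to 5.625%, the apparent reduction is 1 − 5.625% / control risk. With no true effect it is 1 − 7.5% / control risk.

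| r | k | Control risk | Apparent reduction, true 25% | Apparent reduction, true 0% |
|---|---|---|---|---|
| 10% | 0.5 | 7.125% | 21.1% | −5.3% |
| 10% | 1.5 | 7.875% | 28.6% | 4.8% |
| 30% | 0.5 | 6.375% | 11.8% | −17.6% |
| 30% | 1.5 | 8.625% | 34.8% | 13.0% |
| 50% | 0.5 | 5.625% | 0% | −33.3% |
| 50% | 1.5 | 9.375% | 40.0% | 20.0% |

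For example, with r = 30% and k = 0.5, control risk is 7.5% × (0.7 + 0.15) = 6.375%, and 1 − 5.625/6.375 = 11.8%. With k = 1 there is no bias at any r.

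**4. What this could do to WP1.2.** Let groups A and B have shares s_A and s_B of coded patients with a reading inside the window, and let referral among those patients be equally likely in both groups. Relative to the NDA, the odds of being in B rather than A among the referred are multiplied by s_B / s_A, whatever the referral rate. If 20% of A and 40% of B lack such a reading (assumed), the ratio is 0.60 / 0.80 = 0.75. B would look under-referred with no inequality in referral at all.

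**The case against.** Several stronger readings are tempting, and the protocol does not support them.

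- **That WP5.2 treats anyone with an NDH code as eligible.** Design 1 calibrates its codes to the programme-specific eligibility codes, uses the same set in both periods, excludes earlier diabetes and puts baseline HbA1c in the score, with high completeness expected.
- **That every comparison group rests on a code alone.** The surveys used in WP1.1 and WP1.2 are defined by measured HbA1c of 42–47 mmol/mol. The WP1.4 phrase "people with a Read code for non-diabetic hyperglycaemia ('NHS DPP eligible' patients), but who have not been referred to the DPP" concerns invitations to qualitative interviews, and no estimate depends on it.
- **That only people with a recent reading could enter.** Self-referral by risk score was added in August 2020.
- **That the 12- or 24-month rule governed every cohort.** It appears only in WP9.3, and the protocol does not say that it applied to the patients in WP1.2 and WP5.2.

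There are also mitigations. WP5.2 plans sensitivity analyses on assumptions about eligibility and methods for unmeasured confounding. Where referral follows diagnosis closely, matching on time of diagnosis brings test dates close together. Requiring a recent test also selects on testing intensity. Finally, index-date detail is often left to the statistical analysis plan, which is not at hand.

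These points narrow the concern but do not remove it. The protocol itself fixes the design 2 matching variables and the WP1.2 denominator, and as written they omit recency. The eligibility sensitivity analyses have no stated content and do not cover WP1. Selecting on recent testing puts controls on the footing that the primary care rule already gives to referred patients.

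**Conclusion.** The point holds for design 2 and for the NDA denominator in WP1.2, and to a lesser degree for design 1's comparison of referred patients with pre-intervention controls. For that last comparison the protocol already concedes selection bias but does not remove this avoidable part.

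Neither the direction nor the size of the bias can be fixed from the protocol. It gives no share of coded patients without a recent in-range reading, and no conversion risk for them. The tables show only that plausible-looking shares could move the design 2 estimate by an amount comparable to the planned effect, either way. A reader might infer that the programme's effect would be overstated, or that it would be erased. Either would require values of r and k that the protocol does not give.

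The conclusion assumes that the WP9.3 rule applied to primary care referrals in the cohorts analysed. If it did not, the asymmetry shrinks, and the protocol should say so.

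**What to change.** 1. Reconcile WP1.2 and WP5.2 with WP9.3: state which entry rule governed which period and which route.
2. Give each design 2 control an index date, for example the referral date of the matched patient.
3. At that date, require of controls no diabetes code and a most recent prior HbA1c or fasting plasma glucose reading in the NDH range, within the window then in force.
4. Apply the same filter to the WP1.2 NDA denominator and to the controls in design 1's referred-patient comparison.
5. Analyse self-referrals by risk score separately, since they may have no reading.
6. Keep the code-only definition as a named sensitivity analysis, and report how many patients the filter removes. That would supply the share now missing.

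The cost is protocol wording and a date filter on test results in the NDA or CPRD. Some controls are lost. The pre-intervention pool is large (71,521 coded cases in 2015–16 against 3,666 needed per group at 1:1), but the protocol claims no such surplus for design 2, so 5:1 matching within practice may not always be reached. The filtered estimate also applies to recently tested patients, which should be stated.
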